11.5 Rationale for Sample Size and Statistical Power

11.5.1 Overview

The sample size for this study is selected to ensure sufficient power (at least 80%) of a two-sided significance test with level of significance $\alpha=0.05$ to detect clinically meaningful differences between EMM and SMM in Phase 2 with respect to the primary outcome. It is shown in *Phase 1: Detectable effects* on page 11-14 that under the proposed study design and under realistic assumptions about the parameters that affect the power of the test for the primary hypothesis in Phase 1, 324 subjects need to be randomized in Phase 2.

Conservative assumptions have been made that about 50% of subjects randomized in Phase 1 will meet the criteria for Phase 1 treatment failure (i.e., will be eligible for Phase 2) and will agree to be randomized in Phase 2. This assumption is based on expecting about 20% overall (average of EMM and SMM) success rate in Phase 1 and expecting about 40% of the treatment failures (about 30% of all randomized subjects) to be unreachable or to refuse to participate in Phase 2. With this conservative estimate of 50% rate of transition from Phase 1 to Phase 2, it is projected that about $2 \times 324 = 648$ subjects will be entered in Phase 1. Therefore, the sample size for Phase 1 is considered pre-determined and the computations below estimate the relative treatment effect (EMM vs. SMM) that can be detected with $n=648$ subjects randomized in Phase 1.

Of note, since the treatment success rate and the Phase 2 refusal rate are unknown, a feasibility phase will be conducted to refine the estimate of this number (refer to Data and Safety Monitoring Plan). If the actual success and refusal rates are such that less than 50% of Phase 1 participants become randomized in Phase 2, recruitment in Phase 1 will continue until sufficient number of subjects ($n=324$) are entered in Phase 2.

11.5.2 Phase 1: Detectable effects

The success rates for SMM and EMM is expected to be 10%-20% (P_{SMM}) and 20%~30% (P_{EMM}), respectively, and the within site correlation will be small ($0 \sim 0.1$). Table 11.1 shows the power for different combination of P_{SMM} and P_{EMM} based on Model 1. The rightmost three columns represent the percentage of subjects enrolled in Phase 1 who will be eligible for Phase 2, drop out in Phase 1 or refuse to enter in Phase 2, and actually enter in Phase 2. Assume the difference between the success

rate between SMM and EMM is about 10%. The proposed sample size (648) gives sufficient power (>80%) to detect the difference with a two-sided test at $\alpha = 0.05$.

Table 11.1 Power for detecting EMM vs. SMM effects in Phase 1 with n=648, and percent of subjects eligible for Phase 2 and percent entering Phase 2 out of the total n=648.

P_{SM} M	P_{EM} M	Difference $P_{EMM} - P_{SMM}$	Odds Ratio ^a	Power	Drop/Ref Rate Phase 1	Eligible for Phase 2 ^b	Entering Phase 2 ^c
0.1	0.15	0.05	1.59	49%	25%	88%	63%
	0.18	0.08	1.98	84%	25%	86%	61%
	0.2	0.1	2.25	95%	25%	85%	60%
0.15	0.2	0.05	1.42	39%	25%	83%	58%
	0.23	0.08	1.69	74%	25%	81%	56%
	0.25	0.1	1.89	89%	25%	80%	55%
0.2	0.25	0.05	1.33	33%	25%	78%	53%
	0.28	0.08	1.56	67%	25%	76%	51%
	0.3	0.1	1.71	84%	25%	75%	50%
0.25	0.3	0.05	1.29	30%	15%	73%	58%
	0.33	0.08	1.48	62%	15%	71%	56%
	0.35	0.1	1.62	80%	15%	70%	55%
0.3	0.35	0.05	1.26	27%	15%	68%	53%
	0.38	0.08	1.43	58%	15%	66%	51%
	0.4	0.1	1.58	80%	15%	65%	50%

a) Odds Ratio = $[P_{EMM}/(1-P_{EMM})]/[P_{SMM}/(1-P_{SMM})]$

b) Eligible for Phase 2 = 1 - overall success rate in Phase 1 = 1 - $(P_{SMM} + P_{EMM})/2$

c) Entering Rate for Phase 2 = Eligible for Phase 2 – Dropout/Refusal Rate in Phase 1.

The table shows that the sample size planned for Phase 1 affords sufficient power to detect differences in success rate between EMM and SMM as small as 10%. It also shows the range of realistic assumptions about success rate in Phase 1 and dropout (unable to locate or refusal to enter Phase 2) in Phase 1 that result in at least 50% of subjects in Phase 1 going into Phase 2.

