11.2 General Analytic Strategy

11.2.1 Significance Testing

All hypotheses will be tested by two-sided tests with level of significance $\alpha=0.05$. All exploratory analyses will be reported as such and will be thoroughly described in any publication. In particular, the modeling strategy for identification of predictors of outcome (such as inclusion of multiple covariates and interactions) will be explained in detail to allow adequate assessment of the strength of inferences based on data-driven statistical models.

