11.3.3.2 Sample size

Approximately 648 subjects will enter Phase 1. Starting after the second week, they will be monitored for meeting the treatment failure criteria (see *Primary Outcome Measures* on page 11-5) (needle use would indicate failure prior to Week 2). At any time of meeting failure criteria, participants will be given the option to transition from Phase 1 to Phase 2. However, failures can elect to remain in Phase 1 through Week 12 follow-up and can transition to Phase 2 at any time up until the conclusion of Phase

1. Approximately 20% (average over EMM and SMM) are expected to be treatment successes, and about 30% are expected to drop out or refuse entry into Phase 2.

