	0.40	0.55	0.15	1.36
	0.45	0.60	0.15	1.32
	0.50	0.64	0.14	1.29
1.90	0.20	0.32	0.12	1.61
	0.25	0.39	0.14	1.55
	0.30	0.45	0.15	1.50
	0.35	0.51	0.16	1.44
	0.40	0.56	0.16	1.40
	0.45	0.61	0.16	1.35
	0.50	0.66	0.16	1.31
2.00	0.20	0.33	0.13	1.67
	0.25	0.40	0.15	1.60
	0.30	0.46	0.16	1.54
	0.35	0.52	0.17	1.48
	0.40	0.57	0.17	1.43
	0.45	0.62	0.17	1.38
	0.50	0.67	0.17	1.33

Figure 11.2, page 18 shows how the P_{SMM} , odds ratio, total sample size, and correlation within site (ρ) affect the power. Here, the following assumptions were conservatively made:

- The substantial improvement rate in the SMM group is between 30% and 50%.
- The correlation for each pair of responses (substantial improvement) from the same site is about 0.1.
- Between 20 and 30 patients are recruited from each site.

Figure 11.2 Odds Ratios

Top left: Power vs. the correlation for each pair of the substantial improvement rate from the same site (ρ) given site # = 12, sample size per site = 27, $P_{SMM} = 0.30$ and odds ratio = 1.8, 1.9 and 2.0.

Top right: Power vs. P_{SMM} given site # = 12, sample size per site (Phase 2) = 27, $\rho = 0.1$ and odds ratio = 1.8, 1.9 and 2.0.

Bottom left: Total sample size vs. Power given site # = 12, $P_{SMM} = 0.30$, $\rho = 0.1$, and odds ratio = 1.8, 1.9 and 2.0.

This figure conveys at least 80% power to detect an odds ratio of 1.9 between EMM and SMM group or to detect that the difference in substantial improvement rate between two groups is greater than 16% with $324 = 12 \times 27$ total patients enrolled in Phase 2. If the conservative assumption is made that about 50% subjects enrolled in Phase 1 will actually enroll in Phase 2, then the required sample size in Phase 2 is equivalent to a total sample size 648 in Phase 1.

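### Table 11.1: the last row overstates power (about 76%, not 80%), and its 25%/15% drop/refusal rates contradict the 30% behind the 648 projection

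*Protocol*

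**What the plan says.** Section 11.3.3.2 states: "Approximately 648 subjects will enter Phase 1". It expects about 20% successes averaged over the arms, and "about 30% are expected to drop out or refuse entry into Phase 2". Section 11.5.1 builds the 648 on the same basis. It takes 20% success and expects "about 40% of the treatment failures (about 30% of all randomized subjects) to be unreachable or to refuse to participate in Phase 2", which leaves a 50% transition rate and 2 x 324 = 648. It calls that rate conservative, and section 11.5.3 repeats the word. Section 11.4.3.2, by contrast, gives about 50% simply as what is expected.

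Section 11.5.2 expects success of 10%-20% on SMM and 20%-30% on EMM, and says 648 gives more than 80% power for a difference of about 10 points. Table 11.1 then lists 15 scenarios. Its drop/refusal column is 25% for SMM 0.10 to 0.20 and 15% for SMM 0.25 and 0.30. Its last row, 0.30 vs 0.40, shows an odds ratio of 1.58 and power of 80%. The text below says that 648 "affords sufficient power to detect differences in success rate between EMM and SMM as small as 10" per cent, and that the table covers realistic assumptions "that result in at least 50% of subjects in Phase 1 going into Phase 2".

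For Phase 2, section 11.5.3 lists among its conservative assumptions: "The correlation for each pair of responses (substantial improvement) from the same site is about 0.1".

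**The concern.** The table is the only support shown for two statements: that 648 suffices for a 10-point difference in Phase 1, and that half of Phase 1 can be expected to enter Phase 2. The first is read from a row whose odds ratio and power do not follow from the success rates printed beside them. The second is shown only with loss rates lower than the one the text assumes, and the drop from 25% to 15% comes without a reason at the point where 25% would take entry below 50%.

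At stake are the stated Phase 1 power, the 648 projection, and the site commitments built on it: 54 per site at 12 sites, about three a month for 18 months (section 5.2.2). The feasibility review in section 4.4 looks at the Phase 1 failure rate and uptake into Phase 2, and needs one benchmark to compare them with.

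**Working it through.** **Inputs.** Two-sided alpha 0.05 (section 11.2.1). N = 648, taken as 324 per arm; the ratio is not stated, but 1:1 reproduces the table. Success rates, odds ratios and entry formula come from Table 11.1 and its footnotes. Drop/refusal of 30% comes from sections 11.3.3.2 and 11.5.1.

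**Power: reproducing the plan first.** Power = Phi(|pE - pS| / sqrt[(pS(1-pS) + pE(1-pE))/324] - 1.96), with zero within-site correlation.
- 0.20 vs 0.30: 0.10 / sqrt(0.37/324) = 2.959; Phi(0.999) = 84.1%. The table says 84%.
- 0.25 vs 0.35: 0.10 / sqrt(0.415/324) = 2.794; Phi(0.834) = 79.8% (79.5% with a pooled null variance). The table says 80%.
- Fourteen of the 15 entries agree within one point in this way.

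**The last row.** 0.30 vs 0.40: 0.10 / sqrt(0.45/324) = 2.683; Phi(0.723) = 76.5% (76.2% pooled; 75.9%-76.5% over the usual two-sided forms without continuity correction). The table says 80%. By footnote a, the odds ratio is (0.40/0.60)/(0.30/0.70) = 1.556, not 1.58. An odds ratio of 1.58 corresponds to EMM of about 0.404 and power of about 79%, so the row looks as if it was computed for a slightly larger effect than it displays. A within-site correlation of 0.1 would bring this row to about 80%, but would also give 87% at 0.20/0.30 against the stated 84%, so it does not explain the table. For 80% power at 0.30/0.40, about 712 subjects are needed.

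**Entry into Phase 2.** Footnotes b and c: entry = 1 - (pS + pE)/2 - drop/refusal. Phase 1 N needed = 324 / entry. The 10-point rows are:

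| SMM/EMM | Table loss | Table entry | Entry at 30% loss | N for 324 |
|---|---|---|---|---|
| 0.10/0.20 | 25% | 60% | 55% | 590 |
| 0.15/0.25 | 25% | 55% | 50% | 648 |
| 0.20/0.30 | 25% | 50% | 45% | 720 |
| 0.25/0.35 | 15% | 55% | 40% | 810 |
| 0.30/0.40 | 15% | 50% | 35% | 926 |

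At 30% loss, 9 of the 15 rows fall below 50%: all those with SMM 0.20, 0.25 or 0.30. The three with SMM 0.20 lie inside the expected range and give 47.5%, 46% and 45%, needing about 682, 704 and 720.

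**The text's own two versions.** 40% of the 80% who fail is 32% of all randomised, not 30%. Taken literally, entry is 80% - 32% = 48% and N = 324/0.48 = 675.

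**Within-site correlation (minor).** Sections 11.3.3.1 and 11.4.3.1 randomise within site. With an exchangeable correlation rho and a treatment effect constant over sites, the variance of the contrast is multiplied by (1 - rho), so a positive rho raises power. For Phase 2, with SMM 0.30 and odds ratio 1.9, EMM is 0.449. With 162 per arm, power is 79%-80% at rho = 0 and 83%-84% at rho = 0.1.

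**The case against.** The strongest reply is that little depends on these figures. Sections 1.2 and 11.5.1 continue Phase 1 recruitment until 324 have entered Phase 2, so a transition rate below 50% costs time and enrolment, not Phase 2 power. A reader might infer that Phase 2 would run with only 292 subjects (45% of 648) and lose power. The plan rules that out.

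A reader might also infer that Phase 1 is underpowered. That does not follow either. The faulty power row lies outside the expected success range, and within it the 10-point rows have 84%-95%. Drop/refusal does not touch Phase 1 power, because section 11.3.3.3 counts dropouts as failures and all randomised subjects are analysed.

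It is fair, too, that the entry column is presented as a set of scenarios reaching 50%, that six of the nine short rows lie outside the expected range, and that the 32% may be no more than rounding of two approximate figures. Nor is 648 simply too small: at 0.10/0.20 with 30% loss, 590 would do.

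On the correlation, Figure 11.2 is not available here, so what the plan shows at lower values cannot be judged. The gap to 80% at rho = 0 is at most about one point, which does not support calling Phase 2 underpowered.

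What this leaves standing: the last row is wrong as printed, the loss rate differs between text and table without explanation, and the base case has no margin that would justify the word conservative.

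**Conclusion.** Both errors in Table 11.1 are confirmed. The last row should read odds ratio 1.56 and power of about 76%. The claim of more than 80% power for a 10-point difference is sound for SMM success of 10%-20%, marginal at 0.25/0.35 (79.5%-79.8%) and false at 0.30/0.40.

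At the text's 30% drop/refusal, the 50% transition rate is the expected value at 20% overall success. At the upper end of the plan's own range (0.20/0.30) it is 45%, which means 720 subjects, or 720/12 = 60 per site. At three a month that is 20 months against the planned 18.

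Only the stated power, the 648 projection and the site targets are affected. These results assume 1:1 allocation and zero within-site correlation, the setting that reproduces the rest of the table. The correlation point is minor: 0.1 is favourable rather than conservative under within-site randomisation.

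**What to change.** In section 11.5.2 and Table 11.1:
- Correct the last row to odds ratio 1.56 and power 76%.
- Limit the claim of more than 80% power for a 10-point difference to SMM success up to 20%, noting about 80% at 25%.
- Use one drop/refusal rate of 30% in text and table, or give the reason for 25% and 15%.

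In sections 11.5.1 and 11.5.3, drop the description of the 50% transition rate as conservative, and reconcile 40% of failures with 30% of all randomised. State projected Phase 1 enrolment for 10-point differences in the expected range as about 590-720, with 648 at the base case, and carry that range into the site targets.

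In section 11.5.3, take the correlation of 0.1 off the list of conservative assumptions and add that Phase 2 power at zero correlation, odds ratio 1.9 and SMM 30% is about 79%-80%.

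The cost is restated figures and a wider planning range for sites. Design, analysis and the Phase 2 target of 324 stay as they are.

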11.5.3 Phase 2: Sample Size Determination

The power analysis is based on a test statistic proposed by Liu & Liang (1997). The test statistic is based on generalized estimating equation. The power analysis takes into account the fact that data are

correlated (the measurements of patients from the same site) and that the outcome follows a non-normal distribution.

The test statistic is actually a quasi-score statistic based on the generalized estimating equation. The asymptotic distributions of the test statistic under H0 and H1 are both known. In the analysis, the outcome (the substantial improvement rate) has been assumed to follow a binomial distribution with the marginal mean being a function of the intervention. In this case, under the null hypothesis the test statistic converges to Chi-square distribution with 1 degree of freedom. Under the H1, the test statistic converges to non-central Chi-square distribution with 1 degree of freedom. After the parameters in the linear predictor for the mean and in the covariance matrix of the outcome (the working correlation matrix which does not have to be necessarily exactly correct) are specified, the non-central parameter can be computed and thus the power of the test determined.

Power of the test for difference between the two interventions with respect to their substantial improvement rates is computed for a range of values of the difference and the associated covariance parameters. Based on the model (1), the odds of the substantial improvement, depends on the effect of BUP/NX treatment plus SMM (β_0), the efficacy of the BUP/NX with EMM, and the correlation of responses between sites and within sites (ρ). Usually the correlation between sites is very small, and in our case it is reasonable to assume that it is zero (0). To illustrate the efficacy (of EMM vs. SMM) in different familiar terms, Table 11.2 shows the relationship between substantial improvement rates in SMM and EMM group for fixed odds ratios (1.8, 1.9 and 2.0) and change in the substantial improvement rate in the SMM group (P_{SMM}) from 20% to 50%. The higher the odds ratio, the greater the difference (Diff) and relative risk.

[figure not shown]
Table 11.2 Relationship between Substantial Improvement Rates in SMM and EMM Groups for Fixed Odds Ratio

Odds Ratio	P_{SMM}	P_{EMM}	Diff = $P_{EMM} - P_{SMM}$	Relative Risk (P_{EMM}/P_{SMM})
1.80	0.20	0.31	0.11	1.55
	0.25	0.38	0.13	1.50
	0.30	0.44	0.14	1.45
	0.35	0.49	0.14	1.41
	0.40	0.55	0.15	1.36
	0.45	0.60	0.15	1.32
	0.50	0.64	0.14	1.29
1.90	0.20	0.32	0.12	1.61
	0.25	0.39	0.14	1.55
	0.30	0.45	0.15	1.50
	0.35	0.51	0.16	1.44
	0.40	0.56	0.16	1.40
	0.45	0.61	0.16	1.35
	0.50	0.66	0.16	1.31
2.00	0.20	0.33	0.13	1.67
	0.25	0.40	0.15	1.60
	0.30	0.46	0.16	1.54
	0.35	0.52	0.17	1.48
	0.40	0.57	0.17	1.43
	0.45	0.62	0.17	1.38
	0.50	0.67	0.17	1.33

Figure 11.2, page 18 shows how the P_{SMM} , odds ratio, total sample size, and correlation within site (ρ) affect the power. Here, the following assumptions were conservatively made:

- The substantial improvement rate in the SMM group is between 30% and 50%.
- The correlation for each pair of responses (substantial improvement) from the same site is about 0.1.
- Between 20 and 30 patients are recruited from each site.

Figure 11.2 Odds Ratios

Top left: Power vs. the correlation for each pair of the substantial improvement rate from the same site (ρ) given site # = 12, sample size per site = 27, $P_{SMM} = 0.30$ and odds ratio = 1.8, 1.9 and 2.0.

Top right: Power vs. P_{SMM} given site # = 12, sample size per site (Phase 2) = 27, $\rho = 0.1$ and odds ratio = 1.8, 1.9 and 2.0.

Bottom left: Total sample size vs. Power given site # = 12, $P_{SMM} = 0.30$, $\rho = 0.1$, and odds ratio = 1.8, 1.9 and 2.0.

This figure conveys at least 80% power to detect an odds ratio of 1.9 between EMM and SMM group or to detect that the difference in substantial improvement rate between two groups is greater than 16% with $324 = 12 \times 27$ total patients enrolled in Phase 2. If the conservative assumption is made that about 50% subjects enrolled in Phase 1 will actually enroll in Phase 2, then the required sample size in Phase 2 is equivalent to a total sample size 648 in Phase 1.

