11.2.4 Missing Data and Dropouts

Every possible effort will be made to assess all patients in both Phase 1 and Phase 2. Despite our thorough and proactive approach to taking complete measurements on all randomized study patients at all time points, it is expected that there will be cases when assessments will be incomplete or missing.

Accounting for dropout in the analysis. The primary qualitative outcome measures, success/failure in Phase 1 and substantial improvement (yes/no) in Phase 2 will be determined for all study patients, regardless of whether they completed the treatment in these phases or not (see *Treatment Success/Failure for Dropout and Missing Data* on page 11-7 and *Substantial Improvement Status for Dropout and Missing data* on page 11-10). The analysis of the quantitative outcomes, measuring severity of symptoms and positive/negative weekly urines will be based on generalized linear models and Generalized Estimating Equations (GEE) models [Diggle, PJ, Liang K-Y, and Zeger, SL (1994) *Analysis of Longitudinal Data*, Oxford University Press, Oxford]. The GEE methodology requires no parametric distribution assumption, provides robust inference with respect to misspecification of the covariance, and allows analysis of continuous, categorical, and count data which may be missing for some patients either because of a missed week or due to drop-out. Thus, complete information for all patients is not needed. PROC GENMOD in SAS (2003) will be used to carry out these analyses.

The inferences from incomplete or missing data are valid provided that the missing data are missing at random (Little and Rubin, 1987). “Missing at random” means that the missing mechanism does not depend on the value of the unobserved outcome. Unfortunately, this assumption is untestable in most medical research, as in this study.

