11.2.7 Modeling of Site Effects

The outcomes of subjects from the same site are expected to be correlated. To account for these correlations in the analysis, all tests will be based on Generalized Estimating Equations (GEE) models [Diggle, PJ, Liang K-Y, and Zeger, SL (1994) Analysis of Longitudinal Data, Oxford University Press, Oxford]. GEE approach allows modeling of correlated data that is not necessarily normal, such as the primary outcomes for both Phase 1 and Phase 2. This method is generally robust with respect to misspecification of the correlation structure of the outcome in the sense that it produces unbiased estimates of the parameters in the model for the mean.

The goal of this study is to estimate an overall effect of EMM vs. SMM, rather than to study efficacy in individual sites. There is no evidence that the relative efficacy will differ between sites or that overall efficacy of EMM and SMM will be different in different sites, either for Phase 1 or for Phase 2 study. Therefore, main effects for sites and interaction between sites and treatment will be investigated only as an exploratory analysis.

The GEE approach also allows specification of more than one clustering factor. In this study, in addition to site, repeated measurements over time would constitute another clustering factor. GEE will be used to account for the correlation due to repeated measurements over time and the correlation due to correlation within site.

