11.5.4 Projected Number of Sites and Participants Per Site

Based on the simulation results, given the total sample size of 648, variation in the number of site from five to 20 only affects power slightly. Thus, the projected number of sites and patients per site are based on how many sites are willing to join the study and how many patients each site can recruit. It is assumed that 12 sites will enroll in our study, and each site will be able to recruit 54 patients.

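### The 80% Phase 2 power is a many-site figure; with 12 sites a robust-variance GEE test does not deliver both 80% power and a 5% level, and for the robust score test the number of sites matters

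*Protocol*

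**What the plan says.** Section 11.5.1 sizes the whole trial on the Phase 2 primary comparison: at least 80% power, two-sided, at the 0.05 level. Section 11.5.3 bases the calculation on a GEE quasi-score statistic and states that "under the null hypothesis the test statistic converges to Chi-square distribution with 1 degree of freedom", with a non-central chi-square on 1 degree of freedom under the alternative. It adds that the working correlation need not be exactly right. The stated assumptions are an SMM rate of 30–50% and "The correlation for each pair of responses (substantial improvement) from the same site is about 0.1". The result for 12 sites of 27 is "at least 80% power to detect an odds ratio of 1.9 between EMM and SMM group".

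Section 11.5.4, citing simulations that are not shown, says that "given the total sample size of 648, variation in the number of site from five to 20 only affects power slightly". It then sets the number of sites by who is willing to join.

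On the analysis, section 11.2.7 says that "all tests will be based on Generalized Estimating Equations (GEE) models", and section 11.2.4 says that GEE "provides robust inference with respect to misspecification of the covariance". Sections 11.3.4 and 11.4.4.1 test the treatment coefficient by GEE. They do not say whether the test is score or Wald, which variance estimate it uses, or whether any correction is made for few sites.

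**The concern.** The chi-square limits of a GEE statistic hold as the number of independent clusters grows. Here the clusters are sites, and 12 is few. With an empirical variance, the denominator of the test is estimated from 12 site contributions, and for a score test that denominator also grows with the treatment effect. Power then falls below the limit. A Wald statistic referred to the normal distribution errs the other way and rejects too often under the null.

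The 324 patients in Phase 2, and through the assumed 50% transition rate the 648 in Phase 1, both rest on this one figure. If site number is also believed to be nearly irrelevant, the loss of several sites would be treated as harmless when it might not be.

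**Working it through.** **Inputs.** Two-sided level 0.05 (11.5.1); odds ratio 1.9, SMM rate 0.30 (range to 0.50), within-site correlation ρ about 0.1, 12 × 27 = 324 (11.5.3); randomisation within site (11.4.3.1). The allocation ratio is not stated, so 1:1 is assumed (162 per arm), with equal or near-equal site sizes.

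**Step 1: reproduce the plan's figure.** The EMM odds are 1.9 × 0.30/0.70 = 0.8143, so the EMM rate is 0.8143/1.8143 = 0.449. Arms are compared within site, so the variance of the contrast carries a factor (1 − ρ):

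δ = (0.4488 − 0.30) / √{[0.30·0.70 + 0.4488·0.5512]/162 × (1 − ρ)}

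This is 0.1488/0.0531 = 2.80 at ρ = 0, and 2.80/√0.9 = 2.95 at ρ = 0.1. The non-central chi-square (1 df) then gives about 80% and 84%, or 79% and 83% with the pooled null variance. The plan's figure is reproduced at its own ρ. The number of sites does not enter this formula.

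**Step 2: the same test with an empirical variance and K sites.** Let U be a site's score contribution. The statistic is T = (ΣU)²/ΣU², which can never exceed K. In terms of the one-sample t statistic of the site contributions, t² = (K − 1)T/(K − T). So T > 3.84 is the same as |t| > √{3.84(K − 1)/(K − 3.84)} on K − 1 df:

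- K = 5: √(3.84·4/1.16) = 3.64
- K = 12: √(3.84·11/8.16) = 2.28
- K = 20: √(3.84·19/16.16) = 2.12

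Power follows from the non-central t with the δ above. It was checked by simulation with 20,000 trials per cell and a latent-normal site effect.

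| N = 324, 0.30 vs 0.449 | 5 sites | 12 sites | 20 sites |
|---|---|---|---|
| Formula, ρ = 0 | 36% | 70% | 75% |
| Simulation, ρ = 0 | 36% | 70% | 74% |
| Formula, ρ = 0.1 | 40% | 75% | 79% |
| Simulation, ρ = 0.1 | 38% | 74% | 78–79% |

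At ρ = 0.1 with 12 sites, SMM rates of 0.40 and 0.50 give 76–77% by simulation. The simulated type I error of this test (ρ = 0.1) is about 4% at 12 sites and 2% at 5, so it is conservative.

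**Step 3: N = 648, the total named in 11.5.4.** For 0.20 versus 0.30, Table 11.1 states 84%, which the large-sample formula reproduces at ρ = 0. Simulated power of the robust score test at 5, 12 and 20 sites is 39%, 75% and 79% (ρ = 0), and about 35%, 78% and 83% (ρ = 0.1).

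**Step 4: other tests GEE could mean.** N = 324, SMM rate 0.30; power range for ρ = 0 to 0.1, type I error at ρ = 0.1:

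| Test | Power, 12 sites | Power, 5 sites | Type I error, 12 / 5 sites |
|---|---|---|---|
| Robust score, chi-square | 70–74% | 36–38% | 4.0% / 2.0% |
| Robust Wald, normal | 81–85% | 83–86% | 8.6% / 16% |
| Robust Wald, t on K − 1 df | 71–76% | 55–59% | 4.7% / 5.2% |
| Model-based score, exchangeable | 79–84% | 79–84% | 4.8% / 5.1% |
| Cochran-Mantel-Haenszel by site | 79–83% | 79–84% | about 5% |

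**The case against.** The strongest reply is that the loss depends on a choice the protocol does not make. Neither score versus Wald nor the variance estimate is fixed, and such details may sit in an analysis plan that is not shown. With a model-based variance and the correct exchangeable correlation, both the 80% and the flat site-number statement hold. The textual support for a robust variance is also indirect:

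- The sentence in 11.2.4 follows one about symptom scores and weekly urines, not the binary primary outcomes.
- Section 11.2.7 explains robustness only as unbiased estimation of the mean model.
- The working-correlation remark in 11.5.3 concerns the calculation of the non-centrality parameter.

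This stands, and it is why the conclusion is conditional. It does not dispose of the point. Inference that survives a wrong working covariance needs an empirical variance, so that remains the natural reading of 11.2.4 and 11.5.3. None of the robust tests examined has both a 5% level and 80% power at 12 sites and an SMM rate of 0.30. An analysis plan could choose among them, but it could not make 11.5.3 true for any of them.

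A reader might go further and infer that the 80% is a miscalculation, or that 11.5.4 is simply false. The documents support neither. The 80% follows correctly from the stated large-sample method. Section 11.5.4 rests on simulations that cannot be seen: a model-based test would look flat in them, and so would the power of a robust Wald z test, though with an inflated level. Nor is 70% the fair figure for Phase 2, because it needs ρ = 0 and the protocol assumes about 0.1.

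**Conclusion.** The point holds conditionally. If the primary tests use the empirical between-site variance, then at ρ of about 0.1 and 12 sites the quasi-score test has about 75% power for an odds ratio of 1.9 at an SMM rate of 0.30, and 74–77% over rates of 0.30–0.50. The chance of missing that effect is then roughly 23–26%, not at most 20%. The robust Wald z test reaches the stated power only with a type I error of about 8.6%. For the robust score test the statement in 11.5.4 does not hold: about 38%, 75% and 79% at 5, 12 and 20 sites with N = 324, and about 35%, 78% and 83% with N = 648. For a model-based or site-stratified test both statements roughly hold.

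These figures assume 1:1 allocation within site, near-equal site sizes, and a treatment effect common to all sites on the latent scale. Unequal sites were not examined.

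**What to change.** **Preferred.** Test Hypotheses 1.1 and 2.1 with site as a stratum, by Cochran-Mantel-Haenszel or by logistic regression with site indicators and model-based variance. Randomisation is already within site in both phases. In Phase 2 this holds 5% and gives about 79–85% power at 5, 12 or 20 sites, so 11.5.3 and 11.5.4 become roughly true as they stand. Sections 11.2.6 and 11.2.7, which leave the primary analysis unadjusted and make site effects exploratory, need matching edits. The cost is wording, a re-run of the power calculation, and an odds ratio that is within-site rather than marginal. No patients are added.

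**If robust GEE is kept.** Name the test and the variance estimate, and add a correction for few sites. State the 12-site power and type I error for that choice in 11.5.3. With t on 11 df the power is about 71–76%, so the 80% claim would have to go. In 11.5.4, replace the sentence on 5 to 20 sites with power by number of sites, so that a decision to proceed with fewer sites is made on the right figures.
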